#### **AEs leading to dose modification**

AEs leading to dose modification (reduction/interruption) will be presented by SOC and PT.

#### **AEs leading to discontinuation**

AEs leading to discontinuation will be presented by SOC and PT.

#### **Deaths**

A summary of deaths and cause of death will be provided and a corresponding listing will also be produced.

An overall summary of AEs will be presented including:

Number (%) of patients with at least one AE, number (%) of patients with at least one AE leading to dose modification, number (%) of patients with at least one AE leading to discontinuation, number (%) of patients with at least one AESI, number (%) of patients with at least one SAE.

#### ***Subgroup analyses***

Overall summary of AEs will be analysed in the following subgroups of the FAS:

- Age at enrolment (<75 ; ≥75 years of age)
- Baseline WHO Performance Status (<2; =2)
- Sample Type (Plasma ; Tissue ; Other)
- Brain/leptomeningeal metastases status at baseline (Present ; Absent ; Not Done)

#### **4.2.9 Laboratory evaluations**

When laboratory parameters are collected, they will be assessed by the investigator as normal, abnormal-not clinically significant, abnormal-clinically significant, abnormal-leading to dose modification or abnormal-SAE. Details about abnormality will be summarised in tables by parameter and visit.

#### **4.2.10 ECG**

QTc interval fredericia >470 ms (Yes, No), overall evaluation (Normal, Abnormal) and clinically significance (Yes, No) will be summarised by visit.

#### 4.2.11 **Weight**

Weight (Kg) will be summarised by visit.

#### 4.2.12 **WHO performance status**

WHO performance status (Normal Activity, Restricted Activity, In Bed Less Than or Equal to 50% of the Time, In Bed More Than 50% of the Time, 100% Bedridden, Death) will be summarised by visit.

#### 4.2.13 **Slit Lamp Test)**

Slit Lamp test results (Normal, Abnormal) will be summarised by left and right eyes and by visit.

## 5 **INTERIM ANALYSES**

To provide annual updates of key study measures, interim analyses of the global data will take place annually for the first three years (i.e. at approximately 12, 24 and 36 months from the start of recruitment).

CCI

CCI

A large black rectangular redaction box covering the majority of the page content.

CCI

A large black rectangular redaction box covering the majority of the page content.

CCI

CCI

## **6 CHANGES OF ANALYSIS FROM PROTOCOL**

N.A

## **7 COUNTRY SPECIFIC ANALYSES**

Regional and country level analysis may be performed at the interim analyses and final analysis time points if deemed appropriate.

KM OS analysis and outputs will only be presented for countries that have enrolled a minimum of 150 patients and have at least 60% event maturity to ensure robustness of data for this endpoint.

## 9 APPENDICES

### 1. List of Tyrosine kinase inhibitors

Preferred Name	Generation
AZD3759	1st generation
Gefitinib	1st generation
Epitinib	1st generation
Erlotinib	1st generation
Icotinib	1st generation
Afatinib	2nd generation
Dacomitinib	2nd generation
Pozotinib	2nd generation
EGF816/Nazartinib	3rd generation
Avitinib	3rd generation
Olmotinib	3rd generation
Osimertinib	3rd generation
Rociletinib	3rd generation

## 2. List of Chemotherapies:

Preferred Name
Bleomycin
Capecitabine
Carboplatin
Carmustine
Cisplatin
Cytarabine
Docetaxel
Doxorubicin
Epirubicin
Etoposide
Fluorouracil
Gemcitabine
Gimeracil
Ifosfamide
Irinotecan
Lobaplatin
Nedaplatin
Nimustine
Olaparib
Oteracil
Oxaliplatin
Paclitaxel
Pemetrexed
Platinum compounds
Tegafur
Temozolomide
Teniposide
Uftoral
Vincristine
Vinorelbine
Vorinostat

### 3. List of Immunotherapies:

Preferred Name
Atezolizumab
Avelumab
Durvalumab
Ipilimumab
Nivolumab
Pembrolizumab
Tremelimumab

### 4. List of Antiangiogenic Therapies:

Preferred Name
Anlotinib
Apatinib
Endostatin
Bevacizumab
Fruquintinib
Nintedanib
Ramucirumab
Telatinib

## 5. Death due to disease progression coded terms:

Coded term
Adenocarcinoma of lung
Advanced cancer
Brain metastases
Cancer
Cancer of lung
Disease aggravation
Disease progression
Lung adenocarcinoma
Lung cancer
Lung cancer metastatic
Lung neoplasm
Malignant neoplasm of lower lobe, bronchus or lung, in situ
Meningeal carcinomatosis
Non-small cell lung cancer
Non-small cell lung cancer metastatic
Progression of non-small cell lung cancer
Tumor progression

## 6. Surgeries associated with advanced lung cancer:

Preferred term
Lung lobectomy
Lymphadenectomy
Pulmonary resection
Lung neoplasm surgery
Pneumonectomy
Brain tumour operation
Pleurectomy
Hepatectomy
Adrenalectomy
Bone lesion excision
Vertebroplasty
Brain lobectomy
Internal fixation of spine
Lymphoid tissue operation
Metastases to central nervous system
Pericardial drainage
Pericardial effusion malignant
Pleural adhesion
Pleural decortication
spinal corpectomy
Spinal decompression
Tracheal resection
Tumour excision
Ventriculo-pleural shunt

- **Protocol number:** D5160C00022
- **Document title:** Open Label, Multinational, Multicenter, Real World Treatment Study of Single Agent AZD9291 for Patients with Advanced/Metastatic Epidermal Growth Factor Receptor (EGFR) T790M Mutation-Positive Non-Small Cell Lung Cancer (NSCLC) Who Have Received Prior Therapy with an EGFR Tyrosine Kinase Inhibitor (EGFR-TKI).
- **Version numbers:** SAP Addendum Version 1.0
- **Date of the documents:** 03 Nov 2020
- **NCT number:** NCT02474355

Statistical Analysis Plan 7.0 – Addendum 01  
Study code D5160C00022  
Version 1.0  
Date 03 November 2020

---

**Real World Treatment Study – Statistical Analysis  
Plan (for the final analysis) – Addendum 01**

Drug Substance	AZD9291
Study Code	D5160C00022
Version Number	1.0
Date	03 November 2020

---

---

***Open Label, Multinational, Multicenter, Real World Treatment Study of Single Agent AZD9291 for Patients with Advanced/Metastatic Epidermal Growth Factor Receptor (EGFR) T790M Mutation-Positive Non-Small Cell Lung Cancer (NSCLC) Who Have Received Prior Therapy with an EGFR Tyrosine Kinase Inhibitor (EGFR-TKI)***

---

## AMENDMENT HISTORY

Category: Change refers to	Date	Description of change	In line with CSP? Y (version) / N / NA	Rationale
Efficacy	16 Apr 2020	Add OS swimmer plot for uncommon/compound mutation subgroup	NA	Subgroup of interest for OS
Safety	19 Jun 2020	Add table of AEs with CTCAE Grade $\geq 3$ Add Table of AESIs by outcome Add Table of SAE by causality Add Table of SAE by CTCAE grade Update Table of Hy's Law cases Add Listing of SAEs Add Listing of AESIs Add Listing of Hy's Law cases	NA	Adverse events analysis needs more details
	09 Oct 2020	Add Summary of Serious Adverse Events Leading to Dose Modification by System Organ Class and Preferred Term	NA	

CCI

CCI

Appendices	16 Apr 2020	Recoding of Telatinib in antiangiogenic therapies	NA	Dictionaries updated
-------------------	----------------	------------------------------------------------------	----	-------------------------

## LIST OF ABBREVIATIONS

Abbreviation or special term	Explanation
AE	Adverse Event
AESI	Adverse Event of Special Interest
ALT	Alanine Transaminase
AST	Aspartate Transaminase
BICR	Blinded Independent Central Review
BOR	Best Objective Response
CTCAE	National Cancer Institute Common Terminology Criteria for AEs
DoR	Duration of Response
FAS	Full Analysis Set
ORR	Objective Response Rate
OS	Overall Survival
PT	Preferred Term
SAE	Serious Adverse Event
SAP	Statistical Analysis Plan
SOC	System Organ Class
TBL	Total Bilirubin
ULN	Upper Limit of Normal

## **1 STUDY DETAILS**

This Statistical Analysis Plan (SAP) addendum outlines additional outputs and appendices updates after SAP final version 7.0.

## **2 ANALYSIS SETS**

### **2.1 Definition of analysis set**

#### **Full Analysis Set (FAS)**

The full analysis set is defined the same way as detailed in Section 2.1 of the SAP.

## **3 PRIMARY AND SECONDARY VARIABLES**

### **3.1 Efficacy**

#### **3.1.1 Overall Survival (OS)**

Overall survival is defined the same way as detailed in Section 3 of the SAP.

### **3.2 Safety**

#### **3.2.1 Serious Adverse Events (SAEs)**

SAEs are defined the same way as detailed in Section 3 of the SAP.

#### **3.2.2 Adverse Events of Special Interest (AESIs)**

AESIs are defined the same way as detailed in Section 3 of the SAP.

## **4 ANALYSIS METHODS**

### **4.1.1 Efficacy**

#### ***Overall Survival (OS)***

Overall survival will be summarised by mutation combination subgroup.

Analysis will include the number of exposed patients, the number of deaths, the number of censored patients and the number of patients prematurely censored.

In addition, duration of follow-up will be summarised as defined in Section 4.2.7 of the SAP:

- In all censored patients;
- In prematurely censored patients;
- In all patients.

A swimmer plot for OS will be produced for the uncommon/compound mutation subgroup. The swimmer plot will include all patients with an uncommon/compound mutation and will be ordered by mutation combination. Median OS and 95% confidence intervals for Full Analysis

Set will be reported as reference lines. Censored patients will be identified by a cross at the time of censoring.

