**Subgroup Analyses**

Demographics, OS, PFS, TTD and RR will be analysed in the following subgroups of the FAS:

Subgroup	Demo-graphics	OS	PFS	TTD	RR
• Sex (male ; female)	√	√	√	√	√
• Age at enrolment (<75 ; ≥75 years of age)	√	Summary of cause of death	√	√	√
• Race (White, Black, Asian, and Other).	√		√	√	√
• Ethnicity (Asian, non-Asian).	√	√	√	√	√
• Country of enrolment	√		√	√	√
• WHO Performance Status (<2; =2)	√	√	√	√	√

Subgroup	Demo-graphics	OS	PFS	TTD	RR
• Prior Lines of therapy (one line ; more than one line)	√		√	√	√
• Mutation combinations as defined in section 4.2.3: (T790M only ;Common mutations Uncommon / Compound mutations)	√		√	√	√
• Mutation Status (Any compound mutations with a sample size of at least 50 patients (n≥50))	√		√	√	√
• Sample Type for receptor status assessment (Plasma ; Tissue ; Other)	√	√	√	√	√
• Type of T790M testing (Roche cobas® test on plasma ; Every other test on plasma with at least 50 patients ; Roche cobas® test on tissue ; Every other test on tissue with at least 50 patients)	√		√	√	√
• Brain/leptomeningeal metastases status at baseline (Present ; Absent ; Not Done)	√	√	√	√	√
○ Prior radiotherapy (Y/N) in Brain/leptomeningeal metastases subgroup	√		√		√
• Prior Type of anti-cancer therapy (TKI alone  ; TKI + Other anti-cancer therapy  )	√	√	√	√	√
• Prior Type of TKI (TKI first generation only ; TKI second generation only ; TKI first generation + TKI second generation, TKI first generation and/or second generation + TKI third generation)	√		√	√	√
• Prior chemotherapy (Yes  ; No)	√	√	√	√	√
○ Line of Chemotherapy (First line; Second line; Third line or more)	√		√	√	√

TKI alone does not refer to monotherapy, but only ever having previously received a TKI and no other anti-cancer treatment in the metastatic setting.

 Other anti-cancer therapy includes any anti-cancer treatment other than a TKI, palliative radiotherapies and surgery associated with advanced lung cancer as defined in Appendix 6.

 Subgroup Prior chemotherapy = Yes includes all patients previously treated by chemotherapy other than adjuvant or neo-adjuvant only.

Subgroup	Demo-graphics	OS	PFS	TTD	RR
• Use of TKI in patients with prior first or second line chemotherapy (Yes; No)	√		√	√	√

The subgroup analyses will be based on the values recorded on the CRF.

The subgroup analyses for time-to-event endpoints will be performed only for the subgroups with 20 events or more.

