
The summary of cause of death by age class will include disease under study, AEs not considered related to AZD9291, AEs considered related to AZD9291, Other. Deaths due to disease under study are defined as deaths due to disease progression as defined in the list in Appendix 5.

A swimmer plot for PFS will be produced for the uncommon/compound mutation subgroup and a listing of PFS for patients with T790M + Exon 20 Insertion only will be presented.

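### No Kaplan-Meier OS estimate is specified for the mutation combination subgroups; the planned counts and follow-up durations can reveal unequal follow-up but cannot adjust for it.

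*SAP*

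**What the plan says.** OS is the primary efficacy outcome (protocol 2; SAP 1.3). SAP 4.2.7 summarises it by Kaplan-Meier: median, quartiles and rates at fixed time points.

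The subgroup section of SAP 4.2.7 opens by saying "Demographics, OS, PFS, TTD and RR will be analysed in the following subgroups of the FAS", but the table beneath it is selective. OS is ticked for sex, ethnicity, WHO performance status, sample type, brain/leptomeningeal metastases, prior type of therapy and prior chemotherapy. For the two mutation rows the OS cell is blank, while PFS and TTD are ticked. For age (<75; ≥75) the OS cell reads "Summary of cause of death". A general rule follows: "The subgroup analyses for time-to-event endpoints will be performed only for the subgroups with 20 events or more".

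The addendum (4.1.1) then adds an OS summary by mutation combination: "Analysis will include the number of exposed patients, the number of deaths, the number of censored patients and the number of patients prematurely censored". Next comes "In addition, duration of follow-up will be summarised as defined in Section 4.2.7 of the SAP", for all censored, prematurely censored and all patients. Finally, "A swimmer plot for OS will be produced for the uncommon/compound mutation subgroup", with a cross at each censoring time. The reference lines on that plot are "Median OS and 95% confidence intervals for Full Analysis" Set, that is, whole-study values. Neither document lists a Kaplan-Meier curve, median or fixed-time OS rate for a mutation or age group, and neither gives a reason.

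**The concern.** A proportion dead depends on survival and on how long patients were observed. In this study the second varies by design. Protocol 10.2.4 closes each country within 90 days of national reimbursement or, failing reimbursement, within 18 months of its last enrolment. SAP 4.2.7 counts a move to commercial supply as premature censoring. If follow-up differs between mutation groups, their death counts will differ even where survival does not.

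Follow-up durations placed beside the counts let a reader notice this, but do not yield an adjusted figure. At stake is the primary efficacy outcome in a classification that the addendum chose to add for OS. The method that handles unequal administrative follow-up is already the SAP's method for OS overall, and for PFS and TTD in these same groups.

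**Working it through.** **1. Reproduce the plan's own figure.** Inputs from SAP 1.3: exponential OS, median 25 months, 1983 events among 3500 patients. The interval is median × exp(±1.96/√events).

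25 × exp(±1.96/√1983) = 25 × exp(±0.0440) = 23.92 to 26.12 months; stated 23.9-26.1. Maturity is 1983/3500 = 56.7%; stated 57%. All 18 intervals in the table agree to within 0.06 month. The event counts cannot be rebuilt, because the shape of accrual is not given (uniform accrual would give 63.3% at a 25-month median).

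**2. Set the planned OS outputs side by side.**

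| Subgroup | OS output planned | PFS and TTD |
|---|---|---|
| Sex, WHO status and the other ticked rows | Kaplan-Meier | Kaplan-Meier |
| Mutation combinations, all groups | Counts and follow-up durations | Kaplan-Meier |
| Uncommon/compound mutations | As above, plus swimmer plot with FAS reference lines | Kaplan-Meier |
| Age <75; ≥75 | Deaths by cause | Kaplan-Meier |

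**3. Effect of follow-up alone on the proportion dead.** Under the plan's exponential model, with every patient followed for f months, the expected proportion dead is 1 − 2^(−f/median).

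| Median OS | f = 12 | f = 18 | f = 24 | f = 36 |
|---|---|---|---|---|
| 21 months | 32.7% | 44.8% | 54.7% | 69.5% |
| 23 months | 30.3% | 41.9% | 51.5% | 66.2% |
| 25 months | 28.3% | 39.3% | 48.6% | 63.1% |

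Going from 12 to 24 months of follow-up adds 20 to 22 points at unchanged survival (48.6 − 28.3 = 20.3; 54.7 − 32.7 = 22.0).

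**4. Can the planned outputs undo this?** Simulate two groups with the same median of 23 months and assumed uniform censoring over 6-30 and 18-58 months (1000 patients per group).

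| | Shorter follow-up | Longer follow-up |
|---|---|---|
| Proportion dead | 40.7% | 66.2% |
| Median follow-up, censored patients (months) | 15.9 | 32.3 |
| Median follow-up, all patients (months) | 12.5 | 20.7 |
| Kaplan-Meier median OS (months) | 23.0 | 23.0 |

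The follow-up rows expose the imbalance; only the Kaplan-Meier row recovers the equal survival. The all-patients duration mixes times to death with times to censoring (SAP 4.2.7), so it is not a clean measure of follow-up either. With 200 patients per group the Kaplan-Meier medians averaged 22.8 and 23.0, and the median was not reached in 7.5% of runs for the shorter-follow-up group. Fixed-time rates are therefore needed as well.

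**5. Precision in small groups.** Same interval formula, median 23 months:

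- 20 events: 23 × exp(±1.96/√20) = 14.8 to 35.7 months.
- 60 events: 17.9 to 29.6 months.
- 100 events: 18.9 to 28.0 months.

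**The case against.** Much can be said for the plan.

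- **The counts do not stand alone.** A reader might infer that OS in the mutation groups is reported by counts only. It is not: follow-up durations are specified, and the uncommon/compound group has individual OS times. This stands. What is missing is an adjusted estimate.
- **The swimmer plot marks censoring with crosses**, the usual guard against reading a short censored bar as an early death. This stands, and removing the FAS lines would be a matter of preference. The group still has no OS estimate of its own to set beside them.
- **The age row is not a survival comparison.** A reader might take it as one distorted by follow-up. The SAP defines it by cause: "The summary of cause of death by age class will include disease under study, AEs not considered related to AZD9291, AEs considered related to AZD9291," and other. The fair statement is that OS by age is not estimated.
- **Mutation category might be thought to depend on the test each country used**, which would tie it to country closure. SAP 4.2.3 treats a mutation not tested for as absent, and protocol 4.1 prefers local laboratories, but neither document links category to country. The point does not rest on this; if such a link existed, Kaplan-Meier would not cure misclassification or differences in country mix.
- **The wording is not exclusive, and the study is descriptive.** The addendum says what the analysis includes, and the introduction to the subgroup table names OS. The blank cells nevertheless favour the reading without Kaplan-Meier. The sponsor may choose its OS subgroups, and several other rows are blank too; but here the addendum did choose to summarise OS.
- **Caution over sparse OS data.** SAP 7 restricts country-level OS curves to countries with at least 150 patients and 60% maturity. That rule covers countries only. The 20-event rule governs subgroups and permits imprecise estimates, but an interval shows the imprecision, which a count does not.

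**Conclusion.** The point holds for the mutation combination subgroups: OS is summarised there without any estimate that accounts for unequal follow-up, although the SAP uses such an estimate for OS elsewhere and for PFS and TTD in these groups. A change should be made. For age, adding OS is optional.

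The size is illustrative. With identical exponential OS and medians of 25 to 21 months, 28-33% would be dead at 12 months of follow-up and 49-55% at 24. The exponential form and the medians are the plan's; the follow-up lengths and censoring windows are assumptions, because the documents give no follow-up by subgroup. A reader might infer that the mutation or age groups do differ in follow-up by about a year; nothing in the documents shows that. Nor is the OS analysis of the full analysis set affected.

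**What to change.** - In the SAP 4.2.7 subgroup table, tick OS for mutation combinations: Kaplan-Meier median and OS rates at the SAP's fixed time points, with 95% confidence intervals, under the existing 20-event rule.
- Cross-refer to this from addendum 4.1.1, and keep the counts and follow-up durations as a supplement.
- Add the subgroup's own Kaplan-Meier median to the swimmer plot where 20 events are reached; the FAS lines may stay.
- Optionally, add the same OS row for age beside the cause-of-death summary.

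The cost is one or two more rows in a Kaplan-Meier subgroup analysis that is already planned. There are two drawbacks. Small groups will give wide intervals, about 15 to 36 months around a 23-month median at 20 events. And Kaplan-Meier assumes uninformative censoring, whereas patients who move to commercial supply are those still judged to benefit (protocol 10.2.4), so any informative censoring remains and should be stated with the results.

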#### 4.1.2 Safety

All the following outputs will be provided in addition to analyses described in Safety analysis methods section of the SAP (Section 4.2.8).

##### **Serious Adverse Events (SAE)**

The following summaries will be provided for all SAEs as defined in the SAP section 4.2.8:

- number (%) of patients reporting SAEs assessed as causally related to AZD9291 by System Organ Class (SOC) and Preferred Term (PT). If causality is missing, assume that the SAE is causally related.
- number (%) of patients reporting SAEs by SOC, PT and maximum CTCAE grade.
- number (%) of patients reporting SAEs leading to dose modification by SOC and PT.

A listing of all SAEs will be produced. SAEs occurring before starting treatment with AZD9291 included in the data listing will not be included in the summary tables of SAEs.

##### **Adverse Events of Special Interest (AESI)**

Summary table of AESIs providing the number (%) of patients experiencing any of the specified terms by outcome will be produced.

A listing of all AESI will also be produced.

The overall summary described in SAP section 4.2.8 will be replaced by an overall summary of AESIs and SAEs including:

- number (%) of patients with at least one AESI or SAE
- number (%) of patients with at least one AESI or SAE causally related to AZD9291
- number (%) of patients with at least one AE leading to dose modification
- number (%) of patients with at least one AE leading to discontinuation
- number (%) of patients with at least one AESI
- number (%) of patients with at least one AESI causally related to AZD9291
- number (%) of patients with at least one SAE.
- number (%) of patients with at least one SAE causally related to AZD9291
- number (%) of patients with at least one AE leading to death
- number (%) of patients with at least one AE leading to death causally related to AZD9291

Note: If causality is missing, assume that the AE is causally related.

##### ***Subgroup analyses***

Overall summary of AESIs and SAEs will be analysed in all subgroups of the FAS as defined in section 4.2.8 of the SAP.

[figure not shown]
[figure not shown]
A summary table of AEs with CTCAE grade  $\geq 3$  providing the number (%) of patients experiencing any of the specified terms will be also produced.

#### 4.1.3 Potential Hy's Law cases

A cross tabulation of number (%) of patients who had any instance of an elevated aspartate transaminase / alanine transaminase (AST or ALT  $\geq 3xULN$ ) with number (%) of patients who had any instance of elevated total bilirubin (TBL  $\geq 2xULN$ ) will be presented in order to evaluate potential Hy's Law cases.

Potential Hy's Law cases will also be presented in a listing.

## 5 INTERIM ANALYSES

## 6 CHANGES OF ANALYSIS FROM PROTOCOL

NA

## 7 APPENDICES

### 1. List of Tyrosine kinase inhibitors

The following list replaces the list provided in Section 9 of the SAP.

Preferred Name	Generation
AZD3759	1st generation
Gefitinib	1st generation
Epitinib	1st generation
Erlotinib	1st generation
Icotinib	1st generation
Afatinib	2nd generation
Dacomitinib	2nd generation
Pozotinib	2nd generation
Theletinib	2nd generation
EGF816/Nazartinib	3rd generation
Avitinib	3rd generation
Olmotinib	3rd generation
Osimertinib	3rd generation
Rociletinib	3rd generation

